8.2 Dose and treatment regimens

[figure not shown]
For Arm A, up to 20 eligible patients will be enrolled, and all patients will receive:

Durvalumab 1500 mg + tremelimumab 75 mg via IV infusion q4w, starting on Week 0, for up to a total of 4 cycles/doses followed by durvalumab monotherapy 1500 mg via IV infusion

q4w, starting after completion of the 4th cycle of combination treatment, until confirmed PD and Investigator confirmation that the patient is no longer receiving clinical benefit from the treatment, or for other discontinuation criteria. If a patient's weight falls to 30 kg or less the patient should receive weight-based after discussion between Investigator and Study Physician, until the weight improves to >30 kg, at which point the patient should start receiving the fixed dosing of durvalumab 1500mg and 75mg tremelimumab q4w (during the combination phase of treatment). The equivalent weight based doses to the fixed doses are 20 mg/kg of durvalumab and 1mg/kg tremelimumab q4w.

In the first cycle of durvalumab + tremelimumab treatment, tremelimumab will be administered first; the durvalumab infusion will start approximately 1 hour (maximum 2 hours) after the end of the tremelimumab infusion. If there are no clinically significant concerns after the first cycle, then, at the discretion of the Investigator, all other cycles of durvalumab can be given immediately after the tremelimumab infusion has finished.

Appendix A Figure 2 Durvalumab + tremelimumab combination therapy dosing schedule

IV Intravenous; q4w Every 4 weeks.

8.2.1 Duration of treatment and criteria for treatment through progression

All treatment will be administered beginning on Day 1 until confirmed PD unless there is unacceptable toxicity, withdrawal of consent, or another discontinuation criterion is met. Treatment through progression will only be considered for arms containing durvalumab +/- tremelimumab.

Progression during treatment

During the treatment period patients may continue receiving therapy in the setting of unconfirmed radiologic progressive disease (PD) according to Response Evaluation Criteria in Solid Tumors version 1.1 (RECIST 1.1), at the Investigator's discretion, until progression is confirmed. A confirmatory scan is required following a RECIST 1.1 overall time point assessment of progression (PD), preferably at the next scheduled visit and no earlier than 4

weeks after the previous assessment of PD. Patients with PD by RECIST 1.1 (unconfirmed and confirmed) who, in the Investigator's opinion, continue to receive benefit from their assigned treatment and who meet the criteria for treatment in the setting of PD may continue to receive their assigned treatment for as long as they are gaining clinical benefit. However, patients will not be permitted to continue immunotherapy if progression occurs after confirmed response (CR or PR as defined by RECIST 1.1) to immunotherapy treatment in the target lesions (regardless of the appearance of new lesions) i.e the response and progression events both occurred in the target lesions while receiving immunotherapy during the same treatment period.

Patients with rapid tumour progression or with symptomatic progression that requires urgent medical intervention (eg, central nervous system metastasis, respiratory failure due to tumor compression, spinal cord compression) will not be eligible for continuing durvalumab ± tremelimumab.

Patients in the durvalumab + tremelimumab combination therapy arm meeting the retreatment criteria below will follow the same treatment guidelines followed during the original treatment period, including the same dose and frequency of treatments and the same schedule of assessments (with the exception of the PK, ADA, tumor biopsies, biomarker samples and optional PGx assessments, which do not need to be collected a second time).

Patients who meet the criteria for retreatment may only receive retreatment once.

Patients receiving the durvalumab + tremelimumab combination therapy arm may undergo retreatment as described below:

Patients who complete the 4 dosing cycles of the combination of durvalumab and tremelimumab portion of the regimen (with clinical benefit per Investigator judgment), but subsequently have evidence of PD during the durvalumab monotherapy portion of the combination regimen, with or without confirmation according to RECIST 1.1, may restart treatment with the combination.

For all patients who are treated through progression and for patients who are restarting durvalumab + tremelimumab the Investigator should ensure that:

- The patient does not have any significant, unacceptable, or irreversible toxicities that indicate continuing treatment will not further benefit the patient
- There is absence of clinical symptoms or signs indicating clinically significant disease progression accompanied by a decline in WHO/ECOG performance status to >1
- There is absence of rapid disease progression or threat to vital organs or critical anatomical sites (eg, central nervous system metastasis, respiratory failure due to tumor compression, or spinal cord compression) requiring urgent alternative medical intervention.

- The patient still fulfills the eligibility criteria for this study with the exception of inclusion criteria numbers 4 and 7, and exclusion criteria number 19.

During the retreatment period, patients in the durvalumab + tremelimumab combination therapy group will resume durvalumab dosing at 1500mg q4w with 75 mg of tremelimumab q4w for 4 doses/cycles each. Patients will then continue with durvalumab monotherapy at 1500mg q4w, beginning at Week 16, 4 weeks after the last dose of combination therapy until disease progression.

Patients who AstraZeneca and the Investigator determine may not continue treatment after PD will be followed up for survival. Patients who have discontinued treatment due to toxicity or symptomatic deterioration, or who have commenced subsequent anticancer therapy, will be followed up until confirmed disease progression and for survival.

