4.2 Exclusion criteria

1. Involvement in the planning and/or conduct of the study (applies to both AstraZeneca staff and/or staff at the study site).
2. Previous enrollment in the present study.
3. Participation in another clinical study with an investigational product (IP) during the last 4 weeks.
4. Prior randomization or treatment in a previous durvalumab and/or tremelimumab clinical study regardless of treatment arm assignment.
5. Concurrent enrollment in another clinical study unless it is an observational (non-interventional) clinical study or the follow-up period of an interventional study.
6. Major surgical procedure (as defined by the Investigator) within 28 days prior to the first dose of IP. Note: Local surgery of isolated lesions for palliative intent is acceptable where this does not affect assessment of target lesions.
7. Any condition that, in the opinion of the Investigator, would interfere with the evaluation of the IP or interpretation of patient safety or study results, including but not limited to ongoing or active infection, symptomatic congestive heart failure, uncontrolled hypertension, unstable angina pectoris, cardiac arrhythmia, interstitial lung disease, serious chronic gastrointestinal conditions associated with diarrhea or psychiatric illness/social situations that would limit compliance with study requirement, substantially increase risk of incurring AEs from the study medications, or compromise the ability of the patient to give written informed consent.
8. Active autoimmune disease, including a paraneoplastic syndrome of autoimmune nature, requiring systemic treatment other than chemotherapy for SCLC, within the past 3 months

or a documented history of clinically severe autoimmune disease or a syndrome that requires or required systemic steroids or immunosuppressive agents.

9. Active or prior documented autoimmune or inflammatory disorders (including inflammatory bowel disease [eg, colitis or Crohn's disease]), diverticulitis with the exception of (diverticulosis), celiac disease, systemic lupus erythematosus, Sarcoidosis syndrome, or Wegener syndrome (granulomatosis with polyangiitis), Grave's disease, rheumatoid arthritis, hypophysitis, uveitis, etc. The following are exceptions to this criterion:
 - Patients with vitiligo or alopecia
 - Patients with hypothyroidism (eg, following Hashimoto syndrome) and stable on hormone replacement
 - Any chronic skin condition that does not require systemic therapy

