 - Patients without active disease in the last 5 years may be included but only after consultation with the Study Physician
 - Patients with celiac disease controlled by diet alone
10. Active infection including tuberculosis (TB) [clinical evaluation that includes clinical history, physical examination and radiographic findings, and TB testing in line with local practice], hepatitis B (known positive hepatitis B virus [HBV] surface antigen [HBsAg] result), hepatitis C, or human immunodeficiency virus (HIV) [positive HIV 1/2 antibodies]. Patients with a past or resolved HBV infection (defined as the presence of hepatitis B core antibody [anti-HBc] and absence of HBsAg) are eligible. Patients positive for hepatitis C virus (HCV) antibody are eligible only if polymerase chain reaction is negative for HCV ribonucleic acid (RNA).
11. Persistent toxicities (>Common Terminology Criteria for Adverse Events [CTCAE] Grade 2) caused by previous cancer therapy. Any unresolved toxicity (National Cancer Institute [NCI] CTCAE Grade >2) from previous anticancer therapy with the exception of alopecia, vitiligo, and the laboratory results defined in the inclusion criteria.
 - Patients with irreversible toxicity not reasonably expected to be exacerbated by treatment with durvalumab or tremelimumab may be included only after consultation with the Study Physician.
 - Patients with Grade >2 neuropathy will be evaluated on a case-by-case basis after consultation with the Study Physician
12. Any concurrent chemotherapy, immunotherapy (eg, a CTLA-4, PD-1, or PD-L1 inhibitor), or biologic or hormonal therapy for cancer treatment. Concurrent use of hormones for

- non-cancer-related conditions (eg, insulin for diabetes and hormone replacement therapy) is acceptable.
13. Receipt of any live attenuated vaccination within 30 days prior to study entry, while receiving durvalumab + tremelimumab, and within 30 days of receiving durvalumab ± tremelimumab.
 14. Current or prior use of immunosuppressive medication within 14 days before the first dose of durvalumab or tremelimumab. The following are exceptions to this criterion:
 - Intranasal, inhaled, topical steroids, or local steroid injections (eg, intra-articular injection)
 - Systemic corticosteroids at physiologic doses not to exceed 10 mg/day of prednisone or its equivalent
 - Steroids as pre-medication for hypersensitivity reactions (eg, computed tomography [CT] scan pre-medication)

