 15. Radiation therapy to the chest and whole-brain irradiation must be completed at least 4 weeks prior to start of study treatment, and patients must have recovered from any acute adverse effects prior to start of study treatment. An exception to this is palliative radiotherapy for bone lesions and must be completed before the first dose of study treatment.
 16. Past medical history of interstitial lung disease, drug-induced pneumonitis, radiation pneumonitis that required steroid treatment, or any evidence of clinically active interstitial lung disease.
 17. History of hypersensitivity to active or inactive excipients of any investigational drug in the study or drugs with a similar chemical structure or class to those investigated in the study.
 18. History of another primary malignancy except for:
 - Malignancy treated with curative intent and with no known active disease ≥5 years before the first dose of study drug and of low potential risk for recurrence
 - Adequately treated non-melanoma skin cancer or lentigo maligna without evidence of disease
 - Adequately treated carcinoma in situ without evidence of disease (eg, cervical cancer in situ)
 19. History of leptomeningeal carcinomatosis.

20. History of active primary immunodeficiency.
21. History of allogenic organ transplantation.
22. Spinal cord compression unless asymptomatic or treated and stable off steroids and anti-convulsants for at least 1 month prior to study treatment.
23. Female patients who are pregnant or breastfeeding or male or female patients of reproductive potential who are not willing to employ effective birth control from screening to 90 days after the last dose of durvalumab monotherapy or 180 days after the last dose of durvalumab tremelimumab combination therapy.

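### The Arm A rule for treatment beyond progression and retreatment waives exclusion 19, which in the current list is leptomeningeal carcinomatosis, with no stated reason

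*Protocol*

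**What the plan says.** Appendix A section 8.2.1 allows two things after progression in Arm A: continuing study treatment, and a single retreatment with durvalumab + tremelimumab for patients who progress during the monotherapy phase. A common list of conditions applies to both groups: "For all patients who are treated through progression and for patients who are restarting durvalumab + tremelimumab the Investigator should ensure that" four conditions hold. The last is that the patient still meets the study's eligibility criteria, "with the exception of inclusion criteria numbers 4 and 7, and exclusion criteria number 19".

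The criteria behind those numbers are in Appendix A sections 4.1 and 4.2:

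- Inclusion 4: progression on, or within 90 days after, first-line platinum, with no further treatment since.
- Inclusion 7: no earlier immune-mediated therapy.
- Exclusion 19: "History of leptomeningeal carcinomatosis".

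Exclusion 2, "Previous enrollment in the present study", is not among the waived criteria.

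Section 8.2.1 also says that "patients will not be permitted to continue immunotherapy if progression occurs after confirmed response", where response and progression were both in the target lesions during the same treatment period. A later paragraph says that patients who completed four combination cycles with benefit and then progress on monotherapy "may restart treatment with the combination".

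**The concern.** A waiver of this kind should release the criteria that study participation itself makes impossible to meet. Two of the three numbers do that. The third removes an entry exclusion for a serious form of central nervous system involvement, in patients whose disease is by definition progressing, and no reason is given. A site that follows the text exactly would not treat leptomeningeal disease as an eligibility bar to further study treatment. A site that assumes a numbering slip would. The rule is operative and bears on patient safety, so two sites should not be able to apply it differently.

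**Working it through.** No arithmetic applies and the plan gives no figure to reproduce. The check is a look-up of each number, followed by a reading of the neighbouring rules.

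**Step 1: the waived numbers against the current Arm A lists.**

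| Waived | Content in Appendix A | Made unmeetable by study treatment? |
|---|---|---|
| Inclusion 4 | Progression on or soon after first-line platinum, nothing since | Yes |
| Inclusion 7 | No prior immune-mediated therapy | Yes |
| Exclusion 19 | Leptomeningeal carcinomatosis | No |

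The Arm A exclusion list runs without a break from 1 to 23, so the mismatch is not an effect of how the text was extracted.

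**Step 2: could the number belong to another list?** Sections 4.1 and 4.2 of the master protocol hold no numbered criteria and only point to the appendices. Exclusion 19 is another primary malignancy in Appendix B and cardiac dysfunction in Appendix C. Neither is a consequence of Arm A treatment, so neither explains the waiver.

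**Step 3: whom would the waiver affect?** Exclusion 19 applies at entry, and Appendix A section 4 allows no exceptions. Waiving it later therefore matters only for leptomeningeal disease that arose or was recognised after entry. Appendix F lists leptomeningeal disease among non-measurable lesions and counts any new lesion as progression. Such a patient could thus come up for a decision under section 8.2.1.

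**Step 4: what else would stop such a patient?** Section 8.2.1 separately requires:

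- no unacceptable toxicity;
- no clinically significant symptomatic progression with performance status worsening above 1;
- no rapid progression, and no threat to critical sites (central nervous system metastasis is an example) that needs urgent alternative intervention.

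Inclusion 3 (brain metastases asymptomatic, or treated and stable), exclusion 7 (investigator's judgement) and exclusion 22 (spinal cord compression) remain in force. Section 4.7 stops treatment at clinical progression. Leptomeningeal disease that is not rapid, does not need urgent intervention and has not worsened performance status is not clearly caught by any of these.

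**Step 5: unwaived exclusions that touch on participation.**

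- Exclusion 2 (present study): could be misread as describing anyone already enrolled.
- Exclusion 4, "Prior randomization or treatment in a previous durvalumab and/or tremelimumab clinical study regardless of treatment arm assignment": concerns a previous study and is not literally met.
- Exclusion 12, "Any concurrent chemotherapy, immunotherapy (eg, a CTLA-4, PD-1, or PD-L1 inhibitor), or biologic or hormonal therapy for cancer treatment": can be read as therapy other than study drug.

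**Step 6: the responder bar and the restart paragraph.** The bar speaks of continuing immunotherapy; the permission speaks of restarting the combination. The restart paragraph neither repeats nor disapplies the bar.

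**The case against.** The strongest reply is that the safeguards in step 4 would stop most patients with leptomeningeal disease, and that the sponsor and the investigator together determine who may not continue after progression. That stands as far as it goes. But those safeguards depend on speed, urgency, symptoms or judgement, whereas the lifted criterion was absolute. A second reply is that the waiver may be deliberate. The text does not exclude this, but it gives no reason, and the central nervous system example in the neighbouring condition makes it less likely.

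A reader might infer three stronger things that the documents do not support.

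- **That exclusion 2 disqualifies every candidate, so nobody could be retreated.** The natural meaning is an earlier, separate enrolment. Master protocol section 4.3 says withdrawn patients cannot re-enter, and section 4.5 bars enrolment into a second arm. A patient continuing or restarting in Arm A stays on the same enrolment. Inclusion 7 is different, because study treatment literally creates the prior exposure it forbids. What remains is a possible misreading.
- **That the plan gives opposite answers for confirmed responders.** The bar is specific and the restart permission is general and conditional, so the first can be read as limiting the second. What is unsettled is whether continuing includes restarting.
- **That the trial's results are at risk.** Under master protocol section 9.4.1.2 the primary response rate uses data up to progression. Overall survival is secondary and descriptive, and section 8.8 leaves the choice of treatment after study drug to the investigator in any case.

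**Conclusion.** The point holds as an unexplained and probably mistaken cross-reference in an operative safety rule. Followed as written, it lifts the leptomeningeal exclusion for progressing Arm A patients, and the remaining conditions cover this only in part. The intended criterion cannot be determined from the document. The version history records that the criteria were moved into the arm appendices, and it refers to the neutrophil growth-factor clarification as Arm A inclusion 5 where that text now sits in inclusion 12. A stale number is therefore plausible, but this is context and not proof.

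In size, the rule can reach only those of up to 40 Arm A patients (Appendix A section 2.8) who are considered for treatment beyond progression. Retreatment is narrower still, since it requires four completed combination cycles with benefit and then progression on monotherapy. The document gives no basis for estimating how many would have leptomeningeal disease. No sample size, error rate or primary response calculation changes. The conclusion rests on reading the number 19 against the current Appendix A list, the only list in the document to which it can sensibly refer.

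**What to change.** The sponsor should reconcile Appendix A section 4.2 with section 8.2.1 and make three changes in the latter:

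1. Name each waived criterion in words, checked against the current Appendix A numbering, and give a reason if the leptomeningeal waiver is intended.
2. State that exclusion 2 refers to an earlier, separate enrolment, if that is what is meant.
3. State whether the bar on continuing after target-lesion progression following a confirmed response also applies to restarting the combination.

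Which criteria to waive, and how the responder bar should apply, are clinical decisions for the sponsor. The cost is a few sentences in an amendment and a clarification letter to sites. No analysis needs to change.

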4.2 Exclusion criteria

Please refer to Appendix A ([Arm A Exclusion criteria](#)), B ([Arm B Exclusion criteria](#)) or C ([Arm C Exclusion criteria](#)) for exclusion criteria for each individual arm of the study.

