4. PATIENT SELECTION, ENROLLMENT, RANDOMIZATION, RESTRICTIONS, DISCONTINUATION, AND WITHDRAWAL

Each patient should meet all of the inclusion criteria and none of the exclusion criteria for this study. Under no circumstances can there be exceptions to this rule.

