4.1 Inclusion criteria

1. Male or female ≥ 18 years at the time of screening.
2. Written informed consent and any locally required authorization (eg, Health Insurance Portability and Accountability Act in the US, EU Data Privacy Directive in the EU) obtained from the patient/legal representative prior to performing any protocol-related procedures, including screening evaluations.
3. Histologically or cytologically documented extensive disease American Joint Committee on Cancer Stage IV SCLC (T any, N any, M1 a/b) at initial diagnosis, also including patients with:
 - T3-4 due to multiple lung nodules that are too extensive or have tumor/nodal volume that is too large to be encompassed in a tolerable radiation plan.
 - Biopsy-proven mixed SCLC and NSCLC histology
 - Brain metastases; must be asymptomatic or treated and stable off steroids and anti-convulsants for at least 1 month prior to study treatment. Patients with suspected brain metastases at screening should have a computed tomography (CT)/magnetic resonance imaging (MRI) of the brain prior to study entry.
4. Patients must have demonstrated progressive disease (PD) either during first-line platinum-based chemotherapy (platinum refractory) or within 90 days of completing platinum-based chemotherapy (platinum resistant), and have not received further treatment apart from first-line platinum-based chemotherapy. Patients should be enrolled within 90 days of progression in order to be accepted into the study.
5. World Health Organization (WHO)/Eastern Cooperative Oncology Group (ECOG) Performance Status of 0 to 1 at enrollment for the first 10 patients recruited to this arm (see Section 6.3.1 of master protocol for WHO/ECOG assessment parameters). This can be extended to Performance Status 0 to 2 if the arm recruits an additional 10 patients.
6. At least 1 lesion, not previously irradiated, that can be accurately measured at baseline as ≥ 10 mm in the longest diameter (except lymph nodes, which must have a short axis ≥ 15 mm) with CT or MRI and that is suitable for accurate repeated measurements as per RECIST 1.1 guidelines.

7. No prior exposure to immune-mediated therapy including, but not limited to, other anti-CTLA-4, anti-PD-1, anti-PD-L1, and anti programmed cell death ligand 2 (anti-PD-L2) antibodies, excluding therapeutic anticancer vaccines.
8. Body weight >30 kg.

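### Arm A's rule for treatment past progression and retreatment waives exclusion 19, which in the current list is leptomeningeal carcinomatosis; the number is probably wrong and should be replaced by a criterion named in words

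*Protocol*

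**What the plan says.** Appendix A 8.2.1 lists conditions the Investigator must check for two groups: patients treated through progression, and patients restarting the combination after progressing on durvalumab monotherapy. The last condition is that the patient still meets the study's eligibility criteria "with the exception of inclusion criteria numbers 4 and 7, and exclusion criteria number 19". The section gives no reason for any of the three waivers.

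The numbers can refer only to the Arm A lists. Master protocol 4.2 contains no criteria of its own; it sends the reader to the appendices "for exclusion criteria for each individual arm of the study". In Appendix A 4.2, number 19 reads "History of leptomeningeal carcinomatosis".

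Two other Arm A criteria concern central nervous system disease, and neither is waived:

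- Inclusion 3: "Brain metastases; must be asymptomatic or treated and stable off steroids and anti-convulsants for at least 1 month prior to study treatment".
- Exclusion 22: "Spinal cord compression unless asymptomatic or treated and stable off steroids and anti-convulsants for at least 1 month prior to study treatment".

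At entry, Appendix A section 4 is strict about all criteria: "Under no circumstances can there be exceptions to this rule". On restarting, 8.2.1 says: "Patients who meet the criteria for retreatment may only receive retreatment once".

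**The concern.** Two of the three waivers have an obvious purpose and the third does not. A patient who has received durvalumab + tremelimumab has had treatment beyond first-line platinum and has been exposed to immunotherapy. Without waivers of inclusions 4 and 7, nobody could continue or restart. Leptomeningeal carcinomatosis is a clinical event, not a consequence of being on study, so the same reasoning does not reach it.

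The waiver also reverses the protocol's own ordering. At entry, leptomeningeal history is an unconditional bar, whereas brain metastases and cord compression are acceptable if free of symptoms or treated and stable. In 8.2.1 the two conditional limits stay and the unconditional one goes.

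This is an operative rule about who may be dosed. An investigator who follows it exactly would not treat leptomeningeal disease, in itself, as a reason to stop immunotherapy at progression or to refuse a second combination course. What is at stake is patient safety and dosing eligibility.

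**Working it through.** No figure in the plan is in question, so the check sets the clause beside the lists it points to.

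**Step 1: map each waived number to the current Arm A list.**

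| Waived number | Criterion (Appendix A 4.1 or 4.2) | Failed because of study treatment? |
|---|---|---|
| Inclusion 4 | Progression on, or within 90 days of, first-line platinum, with nothing given since | Yes: study drug is further treatment |
| Inclusion 7 | No earlier immune-mediated therapy | Yes: study drug is such therapy |
| Exclusion 19 | Leptomeningeal carcinomatosis | No |

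**Step 2: when the waiver can operate.** Section 4 of Appendix A allows no exception at entry, so a patient with known leptomeningeal history should not be in the arm. The waiver therefore matters only where the disease appears, or is discovered, after entry. That can be the very progression at which 8.2.1 is consulted.

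**Step 3: related criteria still in force.** Inclusion 3 and exclusion 22 are not waived. Arms B and C also exclude leptomeningeal history without qualification (Appendix B 4.2, number 20; Appendix C 5.2, number 10), so nothing elsewhere in the protocol suggests a softer view of it.

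**Step 4: what else would stop such a patient.**

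- 8.2.1 bars rapid progression, and symptomatic progression or a threat to critical sites that needs urgent intervention; central nervous system metastasis is its example.
- 8.2.1 bars clinically significant progression accompanied by a fall in performance status to worse than 1, and bars unacceptable toxicity.
- 8.2.1 relies on the Investigator's judgement of benefit, and allows AstraZeneca and the Investigator to decide that a patient may not continue.
- Appendix A 4.7 makes clinical progression a ground for discontinuation, with or without radiological progression.
- Exclusion 7 (conditions the Investigator thinks would interfere or add risk), exclusion 14 (steroids above 10 mg/day of prednisone or equivalent, with listed exceptions) and inclusion 11 (life expectancy of at least 8 weeks) are not waived.

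**Step 5: what remains.** A patient whose leptomeningeal disease needs no urgent intervention, whose performance status is preserved, who is not on steroids above the cap, whom the Investigator judges to be benefiting, and who has no clinical progression. For this patient, nothing in the text as written makes leptomeningeal disease a bar in its own right. The remaining checks are mostly clinical judgement, where entry had a categorical rule.

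**Step 6: is a stale number plausible?** The version history records that the Arm A criteria were reissued as complete sets when the master lists were moved into the appendices. Numbers did move: the version 3 entry calls the criterion on growth factor use for neutrophils Arm A inclusion 5, and it now sits within inclusion 12. This makes a stale reference plausible but does not prove it.

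**The case against.** The strongest reply is that the error is inferred. The clause gives no reason for waiving inclusions 4 and 7 either, so silence about exclusion 19 does not show a mistake, and a deliberate waiver cannot be ruled out. That stands. What is certain is what the text says and that it does not fit the other two waivers.

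The second reply is that the safeguards in Step 4 already stop nearly every patient one would worry about. This also largely stands. They make the gap narrow, and it cannot be shown that even one patient would fall into it. They do not restore the categorical bar.

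The third reply is that simply deleting the waiver could do harm: if 19 is a stale number, the sponsor may need a waiver of some other criterion. Exclusion 2, on previous enrollment in this study, is the kind of criterion a restart clause might be expected to lift, though nothing in the document says it was the one intended. This reply shapes the fix.

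Three stronger readings are tempting and are not supported:

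- **That the waiver doubles tremelimumab exposure.** Retreatment gives "75 mg of tremelimumab q4w for 4 doses/cycles each", so 4 × 75 mg = 300 mg is added to the initial 4 × 75 mg = 300 mg, for a planned maximum of 600 mg. That is what retreatment gives any eligible patient. It does not measure the waiver, and for treatment through progression the clause adds no tremelimumab beyond the planned four doses.
- **That patients with leptomeningeal disease may enter Arm A.** The clause governs only continuation and restart.
- **That the efficacy result is distorted.** The primary ORR uses data up to first RECIST 1.1 progression (master protocol 9.4.1.2), and the clause acts after progression. Nothing in the document supports a claim about OS.

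**Conclusion.** The point holds as a probable cross-reference error in an operative safety rule. Exclusion 19 in the only applicable list is leptomeningeal carcinomatosis; waiving it does not share the logic of the other two waivers; and inclusion 3 and exclusion 22 remain in force beside it. The intended criterion cannot be recovered from the protocol.

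The practical gap is narrow and its frequency cannot be estimated from the document. The primary ORR is unaffected. The conclusion rests on reading the clause against the current Arm A numbering, and on the absence of any stated reason for treating leptomeningeal disease more leniently than brain metastases or cord compression. It would change only if the sponsor confirmed that the waiver was intended and justified it. The correction is worth making because it is specific and cheap, and because a rule on who may receive further immunotherapy should not depend on a criterion number that appears to be wrong.

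**What to change.** Check the cross-reference in Appendix A 8.2.1 against the current Arm A exclusion list. Replace the number 19 with the intended criterion described in words, so that leptomeningeal carcinomatosis is no longer waived for treatment through progression or for retreatment. Describing inclusions 4 and 7 in words in the same sentence would prevent the problem recurring when the lists are renumbered. Do not simply delete the third waiver until it is known whether another criterion was meant.

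If the waiver of leptomeningeal disease was deliberate, say so, give the reason, and state the conditions under which such a patient may continue or restart.

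The cost is one sentence in an amendment. Data collection, sample size and analysis are unchanged.
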